Measures will be administered within a week prior to beginning treatment, in the week following treatment, and at 6-month follow-up (±1 month). A rehabilitation professional blinded to treatment condition will perform the testing. Reliability of the blinded assessors will be monitored by videotaped assessments reviewed by independent raters.

Additional quality metrics that could create apparent differences in effectiveness in clinical populations will also be measured. After completion of participation, we will survey participants to collect qualitative feedback regarding their experiences with the treatment. Participants will be asked about which therapy condition (traditional CI therapy, gaming CI therapy, standard therapy) they would have preferred under ideal (i.e., cost and transportation are not an issue) and realistic (i.e., their current resources are a consideration) conditions. Differential adherence will also be examined by the proportion of therapy sessions attended, hours of mitt use objectively quantified by a sensor in the mitt, hours of game play, and self-reported compliance with home practice.

Outcome measure	Addresses	Pre	Post	6mo
Motor Activity Log	Nonuse for daily activities	X	X	X
WMFT	Motor speed/function	X	х	X
Grip strength of WMFT ⁹⁹	Weakness	Х	х	X
Kinematics	Weakness, range of motion, motor control, ataxia, poor precision, speed, hypertonicity	х	Х	X
Neuro-QOL	Quality of Life	Х	X	X
Activity monitoring	Nonuse for daily activities	Х	X	X
Brief Kinesthesia Test	Sensory proprioception	Х	х	X
Touch Test Monofilaments	Tactile loss	Х	х	X
Montreal Cognitive Assessment (MoCA)	Cognitive screen	Х		

Survey		X	

Recruitment

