Group 2, Gaming CI therapy. This intervention is designed such that physical/occupational therapists manage patients in a consultative role, thus allowing more patients to be served. 5 therapist/client contact hours will occur in the clinic on approximate treatment days 1, 3, 6, and 11 and will focus on treatment elements that cannot be readily addressed through the game (e.g., transfer package with guided problemsolving). The first session with the therapist (2 hours) will involve establishing the behavioral contract, reviewing the Motor Activity Log (from pre-test) with guided problem-solving, and customizing the game to the participant. Thereafter, sessions will focus on review of progress with the home program, modifying game customization as needed, and on treatment elements that cannot be readily addressed through the game (e.g., guided problem-solving portion of the transfer package with ADL practice as needed, establishing home skill assignments collaboratively). Matching the CI therapy delivery schedule, 15 hours of progressive massed motor practice will occur through in-home video game play over 3 weeks. Participants will play the game during times of their choosing. The proposed delivery system thus allows patients access to rehabilitation between episodes of care provided by therapists. This distribution of activities amounts to the same amount of active motor practice as CI therapy (15 hours) and 5 hours of "transfer package" activities, equivalent to that of traditional CI therapy. In lieu of the mitt, the participant will wear an activity monitor biofeedback device for the majority of waking hours. As with traditional CI therapy, the client will agree to an additional 30 minutes per day of individualized task-practice.

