- 2. Instruct them to wear the activity monitors on both arms for 2 days before treatment to establish a baseline of arm use.
- 3. Make sure participant knows to charge them overnight every night.
- 4. Instruct participant to watch CIMT videos on YouTube. Give them the link.

Treatment Day -1 (TD 1)

- 1. Turn video camera on & show participant ID, treatment day, date, and group
- 2. Complete Treatment Received Form
- 3. Introduce the **Treatment Contract** by reading/explaining each component of the therapy. Briefly present the research.
 - discuss the need for massed practice with the weaker arm and limited use of the stronger arm to drive brain plasticity.
 - discuss how quality of life improvements relate directly to the amount of use for daily activities, regardless of motor ability.
- 4. Home Achievement Record portion of Treatment Contract.
 - Compile list of daily activities done on both weekdays and weekends (one list)
 - Photocopy daily activities list prior to categorizing level of involvement of the weaker arm in each task (10 copies). Provide 1 copy to client to complete prior to next session.
 - Discuss involvement of the weaker arm in each task with problem-solving.
- 5. **Caregiver contract**. Provide instruction to family member/caregiver on problem-solving approach. ("You'll notice that I used a particular approach to help clients come up with solutions to some of the barriers to using the weaker arm.")
 - "Say" They come up with a plan. No questioning.
 - "Do" They try it out
 - "Check" To note what worked and what didn't. Revise the plan.
- 6. Ask participant if he/she watched the CIMT videos on YouTube. If they have not yet, assign as homework.
- 7. Ask participant about adverse events during previous session(s) and fill out **Adverse Event Reporting Form** if need be
- 8. Donn the mitt

- 9. Perform ~9 shaping tasks—document on **Task List**, **Shaping Data Sheets**, and **Shaping Graphs** (1 per task)
- Administer the full MAL-all 28 items using the How Well Scale only (add to MAL spreadsheet)
- 11. Turn video camera off and add comments to **Therapist Treatment Recording Log**
- 12. Store the video on the encrypted hard drive under the correct group and session subfolder

Treatment Day- 2 (TD 2)

- 1. Turn video camera on & say participant ID, treatment day, and group
- 2. Check the mitt time and record it on the Task List; donn the mitt. If mitt wear time is low, problem-solve compliance as needed.

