- Administer a half MAL using the How Well Scale only (record responses on MAL spreadsheet)
- 4. Review the Home Achievement Record with the patient
- 5. Perform ~9 additional shaping tasks (different from those on TD 1)—document on **Task List, Shaping Data Sheets**, and **Shaping Graphs** (1 per task)
- 6. Explain the Home Skill Assignment List (HSA) and select the 10 items
- 7. Give the patient the next Home Achievement Record form
- 8. Ask participant about adverse events and fill out **Adverse Event Reporting Form** if need be
- Turn video camera off and add comments to Therapist Treatment Recording Log
 Store the video on the encrypted hard drive under the correct group and session subfolder
- 11. Ask participant if he/she watched the CIMT videos on YouTube. If they have not yet, assign as homework.

Treatment Day- 3 (TD 3-5, 7-10)

- 1. Turn video camera on & say participant ID, treatment day, and group
- 2. Check the mitt time and record it on the Task List; donn the mitt. If mitt wear time is low, problem-solve compliance as needed.
- Administer a half MAL using the How Well Scale only (record responses on MAL spreadsheet)
- 4. Review the HSA
- 5. Review the Home Achievement Record with the patient
- 6. Repeat the 9 shaping tasks from TD1/TD2 (alternating between treatment days); can now consider shaping the tasks –document on Task List, Shaping Data Sheets and Shaping Graphs
- 7. Select the 10 items for the Home Skill Assignment (HSA) list
- 8. Give the patient the next **Home Achievement Record** form

- 9. Ask participant about adverse events and fill out **Adverse Event Reporting Form** if need be
- 10. Ask participant if he/she watched the CIMT videos on YouTube. If they have not yet, assign as homework.
- 11. Turn video camera off and add comments to **Therapist Treatment Recording Log**
- 12. Store the video on the encrypted hard drive under the correct group and session subfolder

Treatment Day- 6 (TD 6)

- 1. Turn video camera on & say participant ID, treatment day, and group
- 2. Check the mitt and record it on the Task List; donn the mitt. If mitt wear time is low, problem-solve compliance as needed.
- 3. Administer a full MAL all 28 items using the How Well Scale only (record responses on **MAL spreadsheet**)
- 4. Review the HSA
- 5. Review the weekend Home Achievement Record with the patient

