- 1. TOTAL PLAY TIME SHOULD BE 15 HOURS OVER 3 WEEKS.
- 2. Occurs in home on participants' own schedule. 1.5 hours per day on 10 treatment days. Participants are encouraged to break this down into at least 3 separate play sessions per day (15-30 min sessions are optimal).
- 3. Missed game play should be made up during off days.

In-clinic Treatment Days ~Days 2, 3, 4 (1 hour)

- 1. Turn video camera on & say participant ID, treatment day, and group
- 2. Check game play compliance
 - a. Click on Report Generator App (cannot be opened behind firewall)
 - b. A black box pops up that says "Input User ID"
 - c. Enter the participant's Game ID under the "Input User ID" prompt (this ID is found on the participant's business card)
 - d. Hit Enter
 - e. Report is generated (it works best if the computer you're working from has Excel)
- 3. Check compliance with smart watch. Review daily movement counts/problem-solve if low use.
- 4. Review in-game MAL with problem-solving.
- 5. Review **Home Achievement Record** with problem-solving.
- 6. **Home Skill Assignment**, 10 items (may be same or different than 1st HSA).
- 7. Remind participant about computerized MAL for next 4 weeks.
- 8. Ask participant about adverse events and fill out **Adverse Event Reporting Form** if need be
- 9. Ask participant if he/she watched the CIMT videos on YouTube. If he/she has not, assign as homework.
- 10. Turn video camera off and add comments to Therapist Treatment Recording Log
- 11. Store the video on the encrypted hard drive under the correct group and session subfolder

Follow-up

MAL administered through REDCap survey or mail if no internet access weekly for 4
weeks.

Checklist Tele-Gaming

Note: Bolded items are separate sheets within the treatment packet to be completed

Prior to Treatment (after pre-test)

- 1. Provide the activity monitors to participants and demonstrate use.
- 2. Instruct them to wear the activity monitors on both arms for 2 days before treatment to establish a baseline of arm use.
- 3. Make sure participant knows to charge them overnight every night.
- 4. Provide the smart watch to participants and demonstrate use (give them the **instructions** to take home with them).
- 5. Instruct them to wear the watch on the less affected arm for 2 days before treatment to establish a baseline of "normal" arm movement counts.
- 6. Have them record the values on the watch right before going to bed on the **Limb Activation Log**.

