- 6. **Home Skill Assignment**, 10 items (may be same or different than 1st HSA).
- 7. Ask participant about adverse events and fill out **Adverse Event Reporting Form** if need be.
- 8. Ask participant if he/she watched the CIMT videos on YouTube. If he/she has not, assign as homework.
- 9. Turn video camera off and add comments to Therapist Treatment Recording Log
- 10. Store the video on the encrypted hard drive under the correct group and session subfolder

Video consultation Days 4, 6, 7, 9, 10 (20 min)

- 1. Turn video camera on & say participant ID, treatment day, and group
- 2. Review in-game MAL with problem-solving. (10 min)
 - a. Click on Report Generator App (cannot be opened behind firewall)
 - b. A black box pops up that says "Input User ID"
 - c. Enter the participant's Game ID under the "Input User ID" prompt (this ID is found on the participant's business card)
 - d. Hit Enter
 - e. Report is generated (it works best if the computer you're working from has Excel)
- 3. Review **Home Achievement Record** with problem-solving (5 min)
- 4. **Home Skill Assignment**, 10 items (may be same or different than 1st HSA). (5 min)
- 5. Remind participant about computerized MAL for next 4 weeks.
- 6. Ask participant if he/she watched the CIMT videos on YouTube. If he/she has not, assign as homework.
- 7. Ask participant about adverse events and fill out **Adverse Event Reporting Form** if need be
- 8. Turn video camera off and add comments to Therapist Treatment Recording Log
- 9. Store the video on the encrypted hard drive under the correct group and session subfolder

Follow-up

1. MAL administered via phone call weekly for 4 weeks. Therapist is to complete the **MAL in follow-up document** each time.

Description of Therapy

What is CI Therapy?

Constraint Induced Movement Therapy or CI therapy is thought to work because it has been shown to produce a large "rewiring" of the brain; that is, after treatment, a larger part of the brain is involved in producing movement of the weaker arm than before therapy. It also has the effect of overcoming a strong tendency not to use the weaker arm ("learned nonuse") that develops in the early post-stroke period.

Research has shown that patients can "learn" to improve the motor ability of the weaker parts of their bodies and thus cease to rely exclusively or primarily on the stronger parts. For this learning and rewiring to occur, two things have to happen:

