- 10. Store the video on the encrypted hard drive under the correct group and session subfolder

Treatment Day 2 (TD 2)

- 1. Turn video camera on & say participant ID, treatment day, and group
- 2. 10 minutes of neuromuscular re-education. Complete **Treatment Log** Day 2.
- 3. 25 minutes of functional training. Complete **Treatment Log** Day 2.
- 4. 15 minutes of progressive strengthening. Complete **Treatment Log** Day 2.
- 5. 10 minutes of reviewing and updating home program. Complete **Treatment Log** Day 2.
- 6. Ask participant about adverse events and fill out **Adverse Event Reporting Form** if need be.
- 7. Turn video camera off and add comments to Therapist Treatment Recording Log
- 8. Store the video on the encrypted hard drive under the correct group and session subfolder

Treatment Day 3 (TD 3)

- 1. Turn video camera on & say participant ID, treatment day, and group
- 2. 10 minutes of neuromuscular re-education. Complete **Treatment Log** Day 3.
- 3. 25 minutes of functional training. Complete **Treatment Log** Day 3.
- 4. 15 minutes of progressive strengthening. Complete **Treatment Log** Day 3.
- 5. 10 minutes of reviewing and updating home program. Complete **Treatment Log** Day 3.
- 6. Ask participant about adverse events and fill out **Adverse Event Reporting Form** if need be.
- 7. Turn video camera off and add comments to Therapist Treatment Recording Log
- 8. Store the video on the encrypted hard drive under the correct group and session subfolder

Treatment Day 4 (TD 4)

- 1. Turn video camera on & say participant ID, treatment day, and group
- 2. 10 minutes of neuromuscular re-education. Complete Treatment Log Day 4.
- 3. 25 minutes of functional training. Complete **Treatment Log** Day 4.
- 4. 15 minutes of progressive strengthening. Complete **Treatment Log** Day 4.
- 5. 10 minutes of reviewing and updating home program. Complete **Treatment Log** Day 4.
- 6. Ask participant about adverse events and fill out **Adverse Event Reporting Form** if need be.
- 7. Turn video camera off and add comments to Therapist Treatment Recording Log
- 8. Store the video on the encrypted hard drive under the correct group and session subfolder

Video Recording Log is the same as for the Self-Gaming Group.

Usual Care Treatment Log

	TREATMENT DAY 1 (2 hours) Date:	TREATMENT DAY 2 (1 hour) Date:	TREATMENT DAY 3 (1 hour) Date:	TREAMENT DAY 4 (1 hour) Date:	
Evaluation	(30 minutes)	N/A	N/A	N/A	

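### The only adverse event question shown sits inside therapist sessions (10 in Groups 1 and 3, 4 in Groups 2 and 4), so recorded events are not comparable for Group 1 v 2 or Group 2 v 3

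*Combined protocol and SAP*

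**What the plan says.** The AE step appears in the treatment materials, arm by arm:

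- **Group 1 (CI therapy checklist).** TD1, TD2 and TD6 each have their own list with an AE step. A shared list headed "Treatment Day- 3 (TD 3-5, 7-10" covers seven more sessions. The TD1 step reads "Ask participant about adverse events during previous session(s) and fill out" the form, and it comes before the mitt and the first shaping tasks.
- **Group 2 (Checklist Self-Gaming).** There is a step on Day 1 and one in the list for "In-clinic Treatment Days ~Days 2, 3, 4 (1 hour". The protocol's Group 2 paragraph says "5 therapist/client contact hours will occur in the clinic on approximate treatment days 1, 3, 6, and 11".
- **Group 3 (Checklist Tele-Gaming).** There is a step on clinic Day 1, on the Day 2 video contact, on clinic days 3, 5 and 8, and under "Video consultation Days 4, 6, 7, 9, 10 (20 min".
- **Group 4 (Traditional Therapy Checklist).** There is a step in each of four lists, ending with "Treatment Day 4 (TD 4".

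On testing, the Measurement section says "Measures will be administered within a week prior to beginning treatment, in the week following treatment, and at 6-month follow-up (±1 month". Neither the measures list, the visit table nor the assessment forms supplied contain an AE item. The weekly contacts in the month after treatment (phone in Groups 1 and 3, survey or mail in Group 2) are shown with the MAL only.

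The Administration section covers who is told of unanticipated problems, not how events are found. The Data Analysis section does not mention harms.

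**The concern.** AE questions are tied to therapist encounters, and the number of encounters is part of what the trial varies. Group 3 is given video contacts so that its encounter count matches Group 1, while Group 2 is not. The opportunity to report an event therefore differs by design in two comparisons that the Research Design section names: Group 1 v 2 and Group 2 v 3. A difference in recorded events there cannot be separated from how often people were asked.

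Timing adds to this. The Game Play instructions say "Missed game play should be made up during off days", so some play or home practice can fall after Group 2's last clinic visit, and no AE question is shown after that. The same holds for anything after TD10 in Group 1, and for the 6 months after treatment in every arm.

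The trial is meant to help patients weigh a home-based therapy against clinic care, and interim findings that bear on safety go to the IRBs. Both uses need harm data collected alike. The efficacy outcomes are not affected.

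**Working it through.** **1. The plan's own figure.** Group 3 is to have 6 video contacts and as many encounters as Group 1. The checklist gives 1 + 5 = 6 video and 1 + 3 = 4 clinic contacts, 10 in all, matching Group 1's ten treatment days. Video time is 1 + 5 × 20/60 = 2.67 hours, against 2.6 stated in the timeline table. The figure reproduces.

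**2. AE questions per participant, if the checklists are followed.**

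- Group 1: 1 (TD1) + 1 (TD2) + 7 (TD3–5, 7–10) + 1 (TD6) = 10
- Group 2: 1 + 3 = 4
- Group 3: 1 + 1 + 3 + 5 = 10
- Group 4: 1 + 1 + 1 + 1 = 4

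The ratio is 10/4 = 2.5. Without the first session, it is 9/3 = 3.

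**3. Days covered by a question, out of 21.** The documents give no calendar dates, so these are assumptions:

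- Treatment days are weekdays from a Monday, so Group 2's days 1, 3, 6 and 11 become calendar days 1, 3, 8 and 15.
- Group 3's clinic contacts (1, 3, 5, 8) fall on those same days, with the video contacts spread between and after: 1, 2, 3, 5, 8, 10, 12, 15, 17, 19.
- Group 1's ten sessions fall in two weeks: 1–5 and 8–12. The TD6 list reviews a weekend record, which fits this, but the protocol's Group 1 paragraph spreads treatment over 3 weeks.

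Two-day recall counts the day of the question and the day before. Full recall counts every day up to the last question.

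| | Group 2 | Group 3 | Group 1 (two weeks) | Group 2 / Group 3 | Group 2 / Group 1 |
|---|---|---|---|---|---|
| 2-day recall | 7 | 17 | 11 | 7/17 = 0.41 | 7/11 = 0.64 |
| Full recall | 15 | 19 | 12 | 15/19 = 0.79 | 15/12 = 1.25 |

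With equal, constant true rates, Group 2 would show about 40% to 80% of Group 3's events. Against Group 1 the sign changes between the two rows. If Group 1's sessions were instead spread like Group 3's contacts, the Group 3 column would apply to it.

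**4. Other recall models (illustrative assumptions), 10 questions v 4.**

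- Each question independently yields a report with probability q. The share with at least one report is 1 − (1 − q)^n. At q = 0.02 this is 18.3% v 7.8%, ratio 2.36. At q = 0.20 it is 89.3% v 59.0%, ratio 1.51. As q tends to 0 the ratio tends to 2.5.
- An event between the first and last question is reported at the next question with probability 0.5^(lag/h). With sessions on days 1–5 and 8–12 against 1, 3, 8 and 15, half-lives of 1, 3, 7 and 14 days give capture ratios of 2.29, 1.47, 1.20 and 1.10. Perfect recall gives 1.0.

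The counts in step 2 are exact. The distortion is not fixed by the documents and runs from none to about 2.5-fold.

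**The case against.** Several counterarguments have force.

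- **Direction.** A reader might infer that Group 2 is bound to look safer than both Group 1 and Group 3. The documents do not support that for Group 1: under full recall and a two-week Group 1 schedule, Group 2 is covered for more days (15 v 12). This stands.
- **Play after the last visit.** A reader might infer that scheduled play continues after Group 2's last AE question. The checklist puts 1.5 hours on each of 10 treatment days, which is the full 15 hours, and the last visit is near treatment day 11. If both use one day count, only make-up or late play and home practice follow. A reading of day 11 as a calendar day, leaving 10 of 21 days afterwards, fits poorly: Group 4 shares the schedule, and its last visit is ideally in week 3. This stands.
- **Absence.** The Adverse Event Reporting Form and the assessment-session checklists mentioned under Handling missing data are not in the file, so one can say only that no question is shown at test visits. Those checklists are described as covering measures, and AEs are not a listed measure. Nor do late events lack any route to the site: participants can report unprompted, and there is a post-test, weekly MAL contact, a participant survey and a record of drop-out reasons. None of these is shown to ask about AEs.
- **Scope.** Group 1 v 3 and Group 2 v 4 have equal counts, no between-arm AE table is planned, and the device was determined to be of non-significant risk. The first narrows the point. The other two lower the stakes, but harms listed by arm would still invite the comparison.

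**Conclusion.** The point holds in a limited form. Following the file gives 10, 4, 10 and 4 AE questions in Groups 1 to 4 and none shown at any common time point, so recorded AEs are not comparable for Group 1 v 2 or Group 2 v 3.

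For Group 2 v 3 the expected tendency is towards fewer recorded events in Group 2: about 40% to 80% of Group 3's count, given the assumed calendar, equal true rates and 2-day to full recall. For Group 1 v 2 neither size nor sign can be stated without the session calendar. Any true difference in harm would be mixed in with these effects.

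This should be corrected. It does not threaten the primary analysis. If the assessment-session checklists already contain a common AE question at the test visits, showing it would largely resolve the matter.

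**What to change.** Add the existing Adverse Event Reporting Form to the post-test and 6-month visits in all four arms. Use one fixed question with a fixed recall period: since pre-test at the post-test, and since post-test at 6 months. Have the participant complete it, or the site coordinator ask it, after blinded testing, so that the assessor does not learn the arm.

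State in the analysis section that any between-arm AE comparison rests on these two collections. Tabulate session-prompted events separately, labelled as unequal in opportunity. Keep the session question for participant care.

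The cost is a protocol amendment and a few minutes at two existing visits, with no new visit or staff. The downside is reliance on 3–4 weeks' recall at the post-test and about 6 months' at follow-up, so mild events may be under-reported. The opportunity to report becomes equal across arms, but recall may still differ somewhat between people prompted 10 times and 4 times. The Group 4 crossover to stand-alone gaming, for which no AE question is shown either, is not covered by this change.
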